8.1 Study Disposition

Completion/withdrawal from the study and completion/discontinuation from treatment, together with reasons for withdrawal from the study or discontinuation from treatment will be listed and the following will also be tabulated:

- Number and percentage of participants who completed the study
- Number and percentage of participants withdrawn from the study and the reported reason for withdrawal
- For the interim analyses, the number and percentage of participants still ongoing in the study will also be presented
- Number and percentage of participants who completed the 16-week treatment period
- Number and percentage of participants who discontinued treatment early and reason for discontinuation

For participants who fail screening, the reasons for screen failure including details on which inclusion/exclusion criteria were not met will be summarised and listed.

The number and percentage of participants enrolled within each region, country and site will be summarised.

For the enrolled population, the number and percentage of participants in each analysis population will be presented. Inclusion/exclusion in each study population will also be listed, together with reasons for exclusion.

The number and percentage of participants with data available for each scheduled visit (including the early termination visit) will be summarised.

Missed visits due to COVID-19 will also be summarised and listed.

8.2 Protocol Deviations

The number and percentage of participants in the full analysis population with at least one significant protocol deviation will be summarised by deviation category.

All protocol deviations will also be listed.

8.3 Demographic and Baseline Variables

Demography data of age, sex, race, ethnicity will be summarised together with height, weight and BMI at screening.

Baseline vIGA score (randomisation stratification factor from the IRT system and CRF data), baseline EASI score and baseline BSA will be summarised.

Time since diagnosis (years) will be summarised.

Separately atopic dermatitis medications taken pre-treatment will be summarised.

8.4 Medical History

Medical history and concurrent illnesses will be captured and coded using the Medical Dictionary for Regulatory Activities (MedDRA®). The dictionary will be updated through the life of the study with version 24.0 used initially.

Concurrent illnesses and medical conditions will be classified as 'current' if the end date is on or after the date of first dose of study drug, or the condition has been marked as ongoing. Otherwise, they will be classified as 'past'.

Past and current medical history will be summarised separately by System Organ Class (SOC) and Preferred Term (PT). Summary tables will contain the number and percentage of patients. A patient who has multiple conditions in the same SOC or with the same PT will be counted only once in the patient counts. Medical history summaries will be sorted by the internationally agreed SOC order (Table 5) and decreasing frequency of PT within SOC in the Total column.

All medical history data will be listed.

8.5 Prior and Concomitant Medications

Medications will be coded according to the World Health Organization Drug Dictionary (WHODD). The dictionary will be updated through the life of the study with the version dated 01Mar2021 used initially. Medical procedures will not be coded.

Concomitant medications are defined as any medications taken during the treatment period or follow-up period after treatment. This includes any medications started before the first dose and ongoing after the first dose. Prior medications are defined as any medication taken before or during the screening period which were stopped before the first dose of study medication.

Missing and partial start and stop dates will be imputed using the rules specified in [Section 7.3.1](#) before classifying therapies as prior or concomitant. If the classification is still ambiguous after missing and partial dates have been imputed, then the medication will be considered concomitant.

Medications will be summarised by WHODD Anatomical Main Group (Level 1), Therapeutic Subgroup (Level 2) and preferred term. The summaries will report incidence within each relevant level so that a participant taking multiple medications coded to the same relevant Level 1, Level 2 or preferred term would only be counted once within the incidence count for that level or term.

Separate summaries will be produced for each of the following:

- Prior medications
- All concomitant medications
- Concomitant medications started pre-treatment
- Concomitant medications during the treatment period (including any which started pre-treatment)
- Concomitant medications started during the follow-up period

All prior and concomitant medications will be listed.

8.6 Treatment Compliance

Treatment compliance will be summarised for the whole 16-week treatment period.

Summary statistics (n, mean, SD, median and range) will be produced together with the number and percentage of participants within each of the categories defined in [Section 5.3.2.1](#). Percentages will use the number of participants who started the treatment period as the denominator.

Data from the dosing diary, drug accountability and the calculated treatment compliance will also be listed.

8.7 Emollient Compliance

Emollient compliance will be summarised for the whole treatment period.

Summary statistics (n, mean, SD, median and range) will be produced together with the number and percentage of participants within each of the categories defined in [Section 5.3.2.2](#). Percentages will use the number of participants who started the period as the denominator.

Data from the daily diary and the calculated emollient compliance will also be listed.

9 Efficacy Analyses

All efficacy analyses outputs will be created separately for cohorts 1-3 and cohort 4.

In addition to the inferential analyses described below, descriptive statistics will be provided to summarize all efficacy endpoints by treatment group.

For categorical variables, summary tabulations of frequency and percentage of participants within each category will be presented.

For continuous variables and duration endpoints, the number of participants, mean, median, standard deviation (SD), minimum, and maximum values will be presented.

For daily time to event endpoints, the number of participants with the event, the number of participants censored will be presented together with Kaplan-Meier estimates of the proportion of responders in each study week, the estimated median and quartiles for time to response. Kaplan-Meier curves of time to event will also be presented.

All efficacy data will be listed, including both individual item scores and calculated questionnaire summary scores.

9.1 Pooling of Placebo Cohorts

For all cohorts 1-3 efficacy analyses, the cohorts 1-3 placebo groups will be pooled into a single 'all placebo' group and will be used as a common control group for the pooled EDP1815 treatment group and each individual EDP1815 treatment group.

For cohort 4 the process is described in the separate SAP Addendum.

9.2 Selection of Additional Covariates

For all cohorts 1-3 efficacy analyses, the covariates described in [Section 7.2](#) will be considered and included in the primary efficacy model 1 described in [Section 9.3.3](#) for the primary estimand if found to be significant ($p < 0.05$). A forward stepwise selection method will be used to include the covariates after the baseline vIGA score and baseline EASI score have already been fitted.

The covariates selected for this primary model will also be used in all other analytical models including covariates.

For cohort 4 the process is described in the separate SAP Addendum.

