11.4.1. Analysis of Primary Estimand

The primary estimand will be analyzed using a logistic regression with parameters for treatment group, baseline IGA score and baseline EASI score.

Body mass index, gender, race, and region will also be considered and included in the model if found to be significant.

The actual and predicted probability of EASI-50 response in each treatment group together with the estimated odds ratios and associated confidence intervals for each treatment difference will be displayed together with p-values for the comparisons of active treatment vs pooled placebo.

Actual and predicted probabilities of EASI-50 at Week 16 for each treatment group will be plotted.

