5.3.4.2 Treatment-Emergent Adverse Events

An adverse event (AE) will be classified as ‘treatment-emergent’ if the onset date/time was on or after the start date/time of study treatment. Where dates or times are missing or partially missing, AEs will be assumed to be treatment-emergent, unless there is clear evidence (through comparison of partial dates/times, see [Section 7.3.1](#)) to suggest that the AE started prior to dosing.

AEs will be classified into the following study phases based on the onset date/time of the AE after any imputations:

- Pre-Treatment Phase: All AEs with onset date/time prior to the first dose of randomised study treatment
- Treatment Phase: All AEs with onset date/time at the time of or after the first dose of randomised study treatment (Day 1) up to and including the date of the last dose of treatment received.
- Follow-up Phase: All AEs with onset date after the date of the last dose of treatment received.

For participants who complete 16 weeks of dosing per protocol, the Treatment Phase will be from Day 1 to the Week 16 visit, and the Follow-up Phase will start after the Treatment Phase and last until their last day in the study. In all cases the day will be assumed to start at 00:00 hours and end at 23:59 hours. Adverse events occurring in both the Treatment Phase and Follow-up Phase are classified as treatment emergent.

The onset phase of all AEs will be included in the relevant data listings.

6 Sample Size

Cohorts 1-3

The sample size was calculated using the assumption that data from the placebo participants in the three cohorts can be pooled prior to comparison with the EDP1815 treatment groups. No adjustments for multiple testing have been made.

The primary efficacy endpoint is the achievement of EASI-50 at Week 16. The pooled placebo response rate is estimated to be approximately 25% and a doubling of this to 50% for EDP1815 would be considered as clinically meaningful.

Using a two-sided test at the 5% level of significance, 58 participants in each treatment group would give 80% power to detect a difference in one of the EDP1815 cohorts compared to the pooled placebo group. There would also be more than 90% power to compare the pooled EDP1815 group to the pooled placebo group.

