Under the assumption of a 20% drop-out of participants prior to Week 16 this will require a total of at least 73 participants to be enrolled in each treatment group. In order to allow for the 3:1 randomisation in each cohort this has been adjusted to 75 participants per treatment group to give a total of 300 participants recruited. With 75 EDP1815 participants and 25 placebo participants in each of the three cohorts.

Cohort 4

Using the same assumptions relating to the placebo rate, clinically meaningful difference, significance level, and drop-out rate as above for Cohorts 1-3, approximately 70 participants are required in each of the EDP1815 8.0×10^{10} and Cohort 4 Matched Placebo groups to provide approximately 80% power in detecting a difference between EDP1815 and placebo in Cohort 4.

In order to allow 50% of the placebo control group to be concurrent controls and 50% to be historic matched controls from Cohorts 1-3, a 2:1 randomization will be used to enroll 70 EDP1815 8.0×10^{10} subjects and 35 placebo participants to Cohort 4.

If sensitivity analyses indicate that pooling of the Cohort 4 placebo group with the Cohort 1-3 matched placebo data is inappropriate, then the power of the comparison between the Cohort 4 EDP1815 and placebo groups is approximately 65% if only Cohort 4 placebo participants could be used in the treatment comparisons.

7 General Considerations

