7.2 Covariates and Subgroups

Subgroups based on baseline severity of disease will be defined as follows:

- Using baseline vIGA score of 3 for efficacy analysis
- Using baseline vIGA score other than 3 for summaries only (2, 4)

For the inferential models defined in [Section 9](#), in addition to the baseline vIGA score and relevant baseline score where applicable, the following covariates will be considered:

- Body mass index (<30 kg/m², ≥30 kg/m²)
- Sex (male, female)
- Race (Non-Hispanic white and Hispanic or Non-White)
- Region (North America, Europe, Asia Pacific)

Covariates selection will be done separately for cohorts 1-3 analyses and cohort 4.

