9.3.1 Primary Efficacy Estimand

The primary efficacy estimand will be the effect of each individual EDP1815 cohort compared to the pooled placebo group on the percentage of participants achieving EASI-50 at Week 16. The population summary measure of interest will be the odds ratio between each active EDP1815 treatment group and pooled placebo.

Intercurrent events will be accounted for in the following manner:

Table 1 Intercurrent Event Strategies for the Primary Estimand (EDPS1)

Intercurrent event		
Use* of Permitted TCS/TCI Therapy or Type 1 Prohibited Medications ¹	Study Discontinuation Before Week 16 Visit or Type 2 Prohibited Medications ² Use	Noncompliance or Unblinding or Other Protocol Deviations Affecting Efficacy Before Week 16

If <28 days before Week 16 visit: Composite strategy Participant will be considered a non-responder
 
If ≥28 days before Week 16 visit: Treatment policy strategy Data will be used as collected
	
If type 2 prohibited medication² used: Composite strategy Participant will be considered a non-responder from the date of medication start
 
If due to related** reason: Composite strategy Participant will be considered a non-responder from the time of treatment discontinuation in case of missing data
 
If due to non-related** reason: While-on-treatment strategy No replacement of missing data (data after treatment discontinuation will be used as collected)
	
Treatment policy strategy: Data will be used as collected

* Consider the last day with therapy for participant before Week 16.

** Treatment discontinuation reasons will be checked. Reasons related to study medication are lack of efficacy, treatment failure, adverse event (if related). Also, withdrawal of consent may be considered related to study medication based on the clarification text provided, that will be assessed by the Evelo team and provided in a separate spreadsheet. Non-related reasons are all other reasons.

¹Prohibited concomitant medications which may affect efficacy requiring the concomitant medication to be immediately discontinued where possible once the use is discovered. Such medications use will be recorded as protocol deviation. Classification will be provided by the sponsor in a separate spreadsheet.

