4.2 Selection of Additional Covariates

The covariates selected for cohorts 1-3 primary model will be used in all cohort 4 analytical models.

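### The primary model's extra covariates are chosen by stepwise significance on the Week 16 outcome, so the data decide which odds ratio is reported; the Cohort 4 covariate rule is also stated in two ways

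*SAP*

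**What the plan says.** The primary summary measure is set in SAP 9.3.1: "The population summary measure of interest will be the odds ratio between each active EDP1815 treatment group and pooled placebo". Treatment, baseline vIGA and baseline EASI are always in the logistic model (SAP 9.3.3).

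For the remaining baseline factors, protocol 11.4.1 says: "Body mass index, gender, race, and region will also be considered and included in the model if found to be significant". It gives no threshold or procedure. SAP 9.2 adds p<0.05 and a direction: "A forward stepwise selection method will be used to include the covariates after the baseline vIGA score and baseline EASI score" have been fitted. SAP 9.3.3 says the candidates are assessed in the primary model itself, which holds treatment group and Week 16 EASI-50. SAP 7.2 codes BMI, sex and race in two levels and region in three.

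SAP 9.2 carries the selected set to all other models that include covariates. Protocol 11.4.2 and 11.4.4 do the same for the supplementary and secondary models, whether or not the factors matter there, and give comparability as the reason.

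For Cohort 4 there are two statements. SAP 7.2: "Covariates selection will be done separately for cohorts 1-3 analyses and cohort 4". SAP Addendum 4.2: "The covariates selected for cohorts 1-3 primary model will be used in all cohort 4 analytical models". SAP 9.2 refers Cohort 4 to the Addendum. The Addendum's change table has two entries, the Bayesian prior and the within-cohort comparison, and neither is this one.

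**The concern.** The plan says that its focus is model estimation of treatment effects (protocol 11.2, SAP 7.6), so the estimate is the main product. An adjusted odds ratio from a logistic model is not collapsible: adding a prognostic covariate changes the quantity estimated even when the arms are perfectly balanced. If the outcome data choose the covariates, they also choose which conditional odds ratio is reported. The confidence interval is then computed as if that model had been fixed in advance.

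The rule also leaves some gaps. SAP 9.2 names no test statistic and, although it calls the method stepwise, no removal criterion. It lists only vIGA and EASI as already fitted, while SAP 9.3.3 implies that treatment is in as well. No blinded selection step is described. That selection uses treatment codes is an inference from SAP 9.3.3; SAP 9.2 does not say so.

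**Working it through.** **1. The plan's own sample size.** Inputs are in SAP Section 6: "The pooled placebo response rate is estimated to be approximately 25% and a doubling of this to 50% for EDP1815"; "Using a two-sided test at the 5% level of significance, 58 participants in each treatment group would give 80% power"; "Under the assumption of a 20% drop-out of participants prior to Week 16". With pooled variance and no continuity correction:

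n = [1.960 × √(2 × 0.375 × 0.625) + 0.842 × √(0.25 × 0.75 + 0.50 × 0.50)]² / 0.25² = 57.7, so 58. Power at 58 is 80.2%. Then 58 / 0.8 = 72.5, so 73, raised to 75. These figures reproduce. At 75 per group, 75 × 0.8 = 60 evaluable per arm, or 240 across the four arms.

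**2. Number of possible primary models.** Four candidates, each in or out: 2⁴ = 16.

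**3. Chance that a noise factor enters.** If none of the four is prognostic and the tests are roughly independent: 1 − 0.95⁴ = 18.5%. Simulation gives 19-21%.

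**4. Simulation of the SAP procedure.** There were 2,000 trials per scenario with 4 × 60 evaluable. Treatment, vIGA and EASI were always in. The candidates entered by forward likelihood-ratio test at 0.05, and one active arm was compared with placebo by Wald test. The documents give no covariate prevalences or strengths, so these are assumptions: BMI ≥30 in 30%, sex 50/50, race 40/60, region 50/35/15, and a log-odds effect of 0, 0.5 or 1.0 per factor. The true conditional odds ratio is 3.0. Entries are vIGA+EASI only / stepwise / all four forced.

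| Assumed log-odds per factor | Median odds ratio | Power, % | Null rejection, % |
|---|---|---|---|
| 0 | 3.17 / 3.18 / 3.25 | 82.1 / 82.2 / 81.6 | 4.8 / 4.6 / 4.8 |
| 0.5 | 2.92 / 3.07 / 3.15 | 77.4 / 78.6 / 79.1 | 4.6 / 5.5 / 5.3 |
| 1.0 | 2.61 / 3.18 / 3.22 | 67.3 / 75.3 / 75.7 | 6.0 / 6.6 / 6.5 |

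The Monte Carlo standard error of the null rates is about 0.5 points. Stepwise and forced differ by at most 0.2 points there. The excess over 5% in the last row is shared by the fixed models, so selection does not cause it. Stepwise and forced power differ by 0.4 to 0.6 points.

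**5. How far selection moves the estimate.** In trials where something is selected (true odds ratio 3.0), the ratio of the stepwise to the vIGA+EASI odds ratio has a 5th-95th percentile range of 0.92-1.19, 0.91-1.29 and 0.89-1.77 for the three strengths. With an assumed odds ratio of 1.8 per factor, no single model is chosen in more than about 10% of trials, and the full set of four is chosen in about 7%.

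**6. Plan against fix.** With response rates of 25% and 50%, and the factors assumed either to be noise or to have an odds ratio of 1.8 each, the stepwise and all-forced models disagree on at least one of the three primary verdicts in about 7-9% of trials.

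**7. Information available for Cohort 4.** Addendum 4.3.2 fits one model with four treatment levels, including Cohort 1 EDP1815. After 20% drop-out: Cohort 4 EDP1815 70 × 0.8 = 56, Cohort 4 matched placebo 70 × 0.8 = 56, Cohort 1 EDP1815 75 × 0.8 = 60, so 172 evaluable. Expected responders: 56 × 0.50 + 56 × 0.25 + 60 × 0.50 = 28 + 14 + 30 = 72.

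**The case against.** **The rule is pre-specified.** The candidates, coding, forced terms, direction and threshold are all written down, which leaves an analyst little discretion. That stands as a defence against post hoc model choice. It does not fix the estimated quantity, which still depends on the outcome.

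**Covariate choice belongs to the estimator.** The population, endpoint, intercurrent-event strategies and summary measure are all fixed in SAP 9.3.1, and predicted response probabilities are reported beside the odds ratio. This is fair in part. But the summary measure is an odds ratio taken from the adjusted model, and the plan names no marginal version, so its meaning changes with the covariates.

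**The effect is small next to sampling error.** At 58 per group, the standard error of the log odds ratio is √(1/14.5 + 1/43.5 + 1/29 + 1/29) = 0.40, giving a 95% interval of about 1.4 to 6.6 around 3.0. This stands.

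**Stronger readings that the documents do not support:**

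- A reader might infer that stepwise selection breaches the 5% level. The simulation shows no material difference from a fixed model.
- A reader might compare the stepwise model with vIGA+EASI only and find that at least one primary verdict changes in 17-18% of trials (odds ratio 1.8 per factor). That base model is neither the plan nor the fix, and the all-forced model departs from it more often still, in about 20%.
- A reader might take SAP 7.2 and Addendum 4.2 to leave the Cohort 4 analysis undefined. SAP 9.2 defers to the Addendum, which says it holds what differs from the main SAP, so the reuse rule most likely governs. Under that rule no Cohort 4 outcome enters the selection.
- A reader might argue for a smaller Cohort 4 set because only 28 + 14 = 42 responders are expected. That counts two groups; the specified model has about 72.

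**Conclusion.** The point holds as a matter of definition and good practice. It is not a demonstrated error-rate problem. A result-dependent step sits inside the headline analysis, the odds ratio can come from any of 16 models, and the interval takes no account of the choice. Removing the step gives one defined odds ratio at essentially the same power and type I error. The 7-9% disagreement on verdicts shows that the choice can matter near the threshold; it does not show that either model is wrong. That figure, and the drift in the odds ratio, rest on assumed prevalences and prognostic strengths.

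The Cohort 4 conflict is mostly an uncorrected sentence in SAP 7.2 and an unlogged change, but two final documents should not state opposite rules. The point is worth correcting and does not threaten the trial.

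**What to change.** - Delete the selection step in SAP 9.2 and 9.3.3 and in protocol 11.4.1. Reword the dependent text in protocol 11.4.2 and 11.4.4, and the references in SAP 7.5, 9.4.1.2 and 9.4.2.2.
- Pre-specify one model: treatment, vIGA, EASI, BMI, sex, race and region, coded as in SAP 7.2 and kept whether or not significant. State a rule for collapsing sparse region levels, to be applied without outcome data.
- Report the model with vIGA and EASI only as a sensitivity analysis.
- Use the same list for Cohort 4, so that all cohorts report an odds ratio conditional on the same factors. Correct SAP 7.2 and Addendum 4.2 to say so, and log the change.

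**Cost.** This is a small amount of protocol and SAP rewording, using baseline data already collected. The 58 per group is unchanged. If all four factors prove to be noise, power falls by under one point; three simulations gave 80.7% to 80.4%, 82.2% to 81.6% and 82.2% to 81.4%.
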